## Treatment adherence

Adherence to the dosing schedule will be assessed at 6, 12, and 18 months by a count of remaining aspirin tablets or an estimate of remaining vitamin D3 oil. Each patient will also receive a diary where they may record the date of any missed doses. The proportion of used tablets (aspirin) and oil (vitamin D3) will be recorded, as will the proportion of daily doses taken.

## Safety endpoints

Toxicity data will be presented as the proportion of patients displaying either mild, moderate, or severe symptoms split by treatment *group* (aspirin: placebo, 100mg, 300mg; vitamin D3: placebo, active). Serious adverse events data will be presented as the proportion of mild, moderate and severe events recorded by treatment group.

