## Sample size

Sample size calculations suggested that 800 men are needed for a future definitive randomised chemoprevention study of standard (300mg) or low dose (100mg) aspirin vs. placebo and/or Vitamin D3 vs. placebo in patients enrolled on an Active Surveillance programme for prostate cancer.

This feasibility trial aims to demonstrate the acceptability and viability of recruitment for this larger study. Data from this trial will be used to determine the number of centres required to enable the larger, 800 patient trial to fully recruit within 4 years. The sample size was chosen to examine acceptance rates and the time required to recruit 102 patients. We plan to recruit 102 patients over 18 months. If the true recruitment rate is 33.3%, approaching 300 individuals, and therefore recruiting ≥100, would achieve 89% power to show that the true recruitment rate is above 25% (using a two-sided binomial proportion test with a 0.05 significance level).

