# Randomisation procedure

The randomisation will be by permuted block randomisation in order to achieve approximate balance across the 6 treatment groups. This randomisation scheme consists of a sequence of blocks such that each block contains a pre-specified number of treatment assignments in random order, for example each treatment occurring twice in a block. The purpose of this is so that the randomisation scheme is balanced at the completion of each block. PROVENT has 3x2 treatment combinations (a block of 6). However, there are two sizes of placebo aspirin to match the active drug: small (100mg size) and large (300mg size) providing an added complication, as this effectively produces eight possible combinations. To maintain the correct balance of drug and placebo, the PROVENT feasibility study will use two blocks of 6 to make a 'Superblock' of 12. In one block of 6 the placebo aspirin will be first small and then large, and in the other block they will be first large and then small. This ensures the correct number and size of placebo aspirin are dispensed, and that all 8 treatment combinations are represented in each superblock. Consequently, twice as many aspirin, as placebo aspirin tablets, are required for the trial.

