## Study period and visits

The study will last for 18 months (plus ≥30 days for pharmacovigilance). Data will be collected at 3-monthly intervals. Secondary endpoint measures will be carried out at the following times:

- MRI taken at baseline and 12 months
- Prostate biopsy at baseline and 12 months for pathology review & CCP score analysis.
- Serum PSA measured at baseline and every 3 months until 18 months
- Serum testosterone, FSH, and LH at baseline and every 6 months until 18 months
- Serum vitamin D3 taken at baseline and every 6 months until 18 months
- Serum calcium at screening and 6, 12, and 18 months

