### Serum vitamin D3 and calcium

The median corrected serum calcium level will be reported for each treatment arm, as well as the proportion of samples >2.65mmol/L (hypercalcaemic). The relationship between serum vitamin D3 and PSA level at 12 months will be quantified using a linear regression model, with log(1+PSA) as the dependent variable. Baseline PSA and serum vitamin D3 measures will be included to adjust for differences between patients.

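### The SAE summary counts events with no stated denominator, and the SAP nowhere plans the number of men with a serious event in each treatment group

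*SAP*

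**What the plan says.** The SAP's Safety endpoints section has two sentences, with different units.

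- Toxicity is summarised per man: "Toxicity data will be presented as the proportion of patients displaying either mild, moderate, or severe symptoms split by treatment" group. The groups are listed as "aspirin: placebo, 100mg, 300mg; vitamin D3: placebo, active".
- SAEs are summarised per event: "Serious adverse events data will be presented as the proportion of mild, moderate and severe events recorded by treatment group".

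The second sentence does not say whether the proportion is taken over the SAEs in that group, over all SAEs in the trial, or over the men in that group. No other section of the SAP plans a count or percentage of men with an SAE.

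Three other statements supply context. Under Sample size: "We plan to recruit 102 patients over 18 months". Under Randomisation procedure, permuted blocks are used "in order to achieve approximate balance across the 6 treatment groups". Under Study period and visits: "The study will last for 18 months", with a further pharmacovigilance period, so one man can have more than one SAE.

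**The concern.** Men are randomised, not events. An SAE table split by treatment group invites the question of what share of men in each group had a serious event. The planned summary does not answer it directly, and on its most natural reading it carries no information on incidence at all. A group with few SAEs and a group with many can show the same percentages.

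At stake is how serious harm is described across the aspirin doses and between vitamin D3 and its placebo. This matters because the trial is meant to inform a definitive study of 800 men. The preceding toxicity sentence shows that a per-man summary was within reach, but that table is classified by symptom severity and is not specific to serious events.

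**Working it through.** The SAP states no SAE rate or expected count, so there is no figure of its own to reproduce. The check sets out the possible denominators and asks what each would show.

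**Inputs from the SAP.** 102 men (Sample size) and approximate balance over 6 groups (Randomisation procedure). Under exact balance:
- per cell: 102/6 = 17 men
- per aspirin level: 17 × 2 = 34 men
- per vitamin D3 level: 17 × 3 = 51 men

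**Inputs that are assumptions.** All SAE counts and all numbers of SAEs per man below.

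**Reading 1: severity mix within a group.** Formula: SAEs of a given severity / all SAEs in that group.
- Group A, 4 SAEs split 1/2/1: 1/4, 2/4, 1/4 = 25/50/25%.
- Group B, 8 SAEs split 2/4/2: 2/8, 4/8, 2/8 = 25/50/25%.
- Men affected at one SAE per man: 4/34 = 11.8% and 8/34 = 23.5%.

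The printed percentages are identical while the share of men affected differs twofold.

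**Reading 2: each group's share of all SAEs.** Formula: SAEs in the group / SAEs in the trial.
- 4, 4 and 8 SAEs in the three aspirin groups: 4/16, 4/16, 8/16 = 25%, 25%, 50%.
- If the 8 SAEs came from 4 men with two each, and the other groups had one SAE per man, the men affected are 4/34 = 11.8% in every group.

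The printed percentages differ twofold while the share of men affected is the same.

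**Reading 3: SAEs per man in the group.** Formula: SAEs in the group / men in the group.
- 8 SAEs: 8/34 = 23.5%.
- One SAE per man: 8 men, 8/34 = 23.5%, which agrees.
- Two SAEs per man: 4 men, 4/34 = 11.8%, which does not.

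This reading does show incidence of events, and it equals the share of men affected when no man has a repeat SAE.

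**If raw SAE counts were printed as well.** The number of men would still be open. With 6 SAEs in one group:

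| Men with an SAE | Share of 34 (aspirin level) | Share of 51 (vitamin D3 level) |
|---|---|---|
| 1 | 2.9% | 2.0% |
| 3 | 8.8% | 5.9% |
| 6 | 17.6% | 11.8% |

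The severity split of the six events could be the same in all three rows.

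**The case against.** The strongest reply is that the SAE sentence may be loose parallel wording. The sentence before it divides by patients in each treatment group, and if the authors meant the same here, the table would give SAEs per man. That shows incidence and, without repeat SAEs, equals the share of men affected. This stands: it would be wrong to infer that the planned table can never give that share. But the sentence says events, the natural reading is a severity split, and nothing in the SAP selects the per-man denominator.

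Second, the examples are constructed. The 1/2/1 and 2/4/2 splits are exactly proportional by choice, and the SAP gives no SAE rate. This also stands. The examples show what the table could hide; they do not show that a distortion is likely.

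Third, the consequence is small. This is a feasibility trial whose primary endpoint is recruitment, and the safety section plans description only. Even 4/34 against 8/34 men gives a two-sided Fisher p of about 0.34, so a per-man table would not separate such groups by a test. That is true, but the purpose of the table is to describe harm, and a description should use an interpretable denominator.

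Fourth, the per-patient toxicity table already meets part of the need. It does, and it would be wrong to say the SAP lacks per-patient safety reporting altogether. What is missing is the figure specific to serious events. This is also not a matter left to the protocol, because the SAP itself fixes the SAE summary.

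A reader might extend the point to the calcium analysis, which reports "the proportion of samples >2.65mmol/L (hypercalcaemic"). That is a legitimate laboratory summary with its unit stated. No error is shown there and no change is asked for.

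**Conclusion.** The point holds as a weakness in how the SAE summary is fixed. The unit is events, the denominator is unstated, and the number of men with an SAE is not planned anywhere in the SAP. Only the events-per-man reading recovers the share of men affected, and only without repeat SAEs.

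No size can be derived from the SAP. In the leading illustration, the same printed 25/50/25% covers 11.8% and 23.5% of men affected. This rests on assumed counts of 4 and 8 SAEs, one SAE per man, and exact balance at 34 men per aspirin level.

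A reader might infer that the trial's safety conclusions would be wrong, or that the comparison of groups would be biased. The SAP does not support this: it plans no test on SAEs, and whether repeat SAEs will occur is unknown. The effect is confined to descriptive safety tables; recruitment results, sample size and efficacy analyses are untouched.

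**What to change.** In the SAP's Safety endpoints section, replace the SAE sentence with a per-man summary. For each aspirin level (placebo, 100mg, 300mg) and each vitamin D3 level (placebo, active), report:

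- the number and percentage of men with at least one SAE, with the men in that group as the denominator, classified by each man's worst severity;
- beside it, the number of SAE events by severity.

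The event-based information is kept, now as counts whose unit is clear.

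The cost is a change of SAP wording and a little extra table work. No new data are needed, and the calcium section stays as it is.
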